17.6.2 ABNORMAL INVOLUNTARY MOVEMENT SCALE (AIMS)

[figure not shown]
The AIMS is a clinician-rated assessment of abnormal movements consisting of unobtrusive observation of the subject at rest (with shoes removed) and several questions or instructions directed toward the subject. It contains seven items related to: facial, lip, jaw, and tongue movements (items 1 -4), upper and lower extremity movements (items 5 - 6), and trunk movements (item 7). Three other items assess the subject at a global level (items 8 - 10), and two items assess dental status (items 11 - 12).

The (non-global) AIMS total score is the sum of items 1 through 7. (Items 8 through 12 are not used in AIMS total score calculation.) The possible range for AIMS total score is 0 to 28. Higher values of the AIMS total score indicate increased severity in abnormal movement. If one or more of the 7 items contributing to AIMS total score calculation are missing at a visit, the total score will be set to missing for that visit.

AIMS total score at each visit is classified as 'abnormal' if: either at least two items (out of items 1 - 7) have a response of 'Mild' or higher (i.e. item score ≥ 2); or at least one item (out of items 1 - 7) has a response of 'Moderate' or higher (i.e. item score ≥ 3). Otherwise, the non-missing AIMS total scores is classified as 'normal'.

Item 8 of AIMS represents the global severity score. Post-Baseline AIMS global severity scores will be classified as 'worsened', 'unchanged', or 'improved', relative to a subject's Baseline response to item 8. A higher score than that of the Baseline would be classified as 'worsened'. Conversely, a lower score would be classified as 'improved'. If the score is equal to that of Baseline, the score will be classified as 'unchanged'.

Document: CCI

Author: PPD

Version Number: 0.6

Version Date: 30JAN2023

Template No.: CS_TP_BS016 Revision 6

Reference: CS_WI_BS005

Effective Date: 02Dec2019

AIMS is assessed at these study visits: Visit 2, Visit 3, Visit 5, Visit 10, and Visit 17.

Change from Baseline in AIMS total score at each scheduled visit (Week 1/Visit 3, Week 4/Visit 5, Week 24/Visit 10, Week 52/Visit 17) will be analyzed using an MMRM similar to the model described in [Section 16.1.1.1](#), with Baseline AIMS total score as the covariate. In addition, the MMRM analysis will be performed for subgroups of subjects based on whether the subject took concomitant medications for treatment of movement disorders during the study, which is similar to the model described in [Section 16.1.1.4](#). The list of medications will be determined by a review of the coded medication terms before database lock and study unblinding.

Change from Baseline in AIMS total score at each scheduled visit (Week 1/Visit 3, Week 4/Visit 5, Week 24/Visit 10, Week 52/Visit 17) will be analyzed using an ANCOVA model similar to the model described in [Section 16.1.1.3](#) (Analysis of covariance (including LOCF)), with Baseline AIMS total score as the covariate.

The observed AIMS total score and the change from Baseline values will also be summarized descriptively by treatment group and visit. In addition, the observed AIMS total score and the change from Baseline values will be summarized descriptively by the subgroups of concomitant medication use for treatment of movement disorders.

Shift from Baseline in AIMS total score category (Normal/Abnormal) to each post-Baseline scheduled visit (Week 1/Visit 3, Week 4/Visit 5, Week 24/Visit 10, Week 52/Visit 17) and to the overall post-Baseline period (including both the double-blind treatment period and the follow-up period up to and including 9 days after the last dose of study drug) will be summarized descriptively by treatment group.

The observed AIMS global severity score and the change from Baseline values will be summarized descriptively by treatment group and visit. In addition, the frequency distribution of the AIMS global severity item will be summarized descriptively by treatment group and visit. Post-Baseline changes in AIMS global severity score (Worsened/Unchanged/Improved) will also be summarized descriptively by treatment group and visit.

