- Clozapine used at 200 mg/day or less for insomnia, agitation, or anxiety must be discontinued at least 28 days prior to randomization. Subjects with a history of treatment with clozapine for any reason at doses greater than 200 mg/day or at doses less than or equal to 200 mg/day for an indication other than insomnia, agitation, or anxiety are excluded from study participation.
- Depot neuroleptics must have been discontinued at least one treatment cycle or at least 30 days (whichever is longer) prior to the randomization visit.

Treatment with the sedative hypnotics described in [Section 10.3.5](#) is permitted during the Screening/Washout Period but should be tapered as clinically appropriate to conform with and

adequately prepare the subject for the protocol-specified limitations applicable to these agents following randomization. Subjects should not be taken off their current effective medications for treatment of schizophrenia for purposes of participating in this study.

Treatment with medications used to treat movement disorders must be discontinued at least 1 day prior to randomization.

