10.3.5. Allowed Concomitant Psychotropic Medications

Treatment with benztropine (benzotropine outside the United States [US]) up to 6 mg/day is permitted, as needed, for motor symptoms. In cases where benztropine is not available or a subject has had an inadequate response or intolerance to benztropine treatment, the following medications may be used to treat acute extrapyramidal symptoms (EPS): biperiden (up to 16 mg/day) or trihexyphenidyl (up to 15 mg/day) or diphenhydramine (up to 100 mg/day). Treatment with propranolol (up to 120 mg/day) is permitted as needed for akathisia. These allowed medications for the treatment of EPS and akathisia may be given in any formulation (oral, intramuscular [IM] or intravenous [IV]) as deemed appropriate by the Investigator. Medications used to treat motor symptoms should not be given prophylactically. They are to be tapered and discontinued 1 day prior to randomization but may be reinstated if symptoms emerge post-randomization during the study.

Concomitant use of lorazepam, temazepam, eszopiclone, zaleplon, zolpidem, zolpidem controlled release (CR), diphenhydramine, and melatonin is permitted at the discretion of the Investigator with the following restrictions:

- Oral lorazepam (or equivalent benzodiazepine) is permitted for clinically significant anxiety/agitation or as a sedative/hypnotic up to a maximum daily dose of 6 mg/day. Intramuscular lorazepam is permitted up to 4 mg/day for acute anxiety/agitation, as clinically indicated. Lorazepam should be used sparingly, when clinically required, per investigator judgment.
- Diphenhydramine \leq 100 mg/day and melatonin \leq 5 mg/day may be administered at bedtime for insomnia, as needed. Over-the-counter melatonin should be used. Combination melatonin products are not allowed.
- Temazepam (\leq 30 mg/day), eszopiclone (\leq 3 mg/day), zopiclone (\leq 7.5 mg/day), zaleplon (\leq 20 mg/day), zolpidem (\leq 10 mg/day), and zolpidem CR (\leq 12.5 mg/day) may be administered at bedtime for insomnia, as needed.
- Medications that are used for insomnia should be administered no more than once nightly and should not be used in combination.
- Medications used for the treatment of anxiety/agitation and insomnia (e.g., lorazepam and zolpidem) should not be used in close temporal proximity (defined as administration within 2 hours of each other).

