13. MEDICATIONS

Unless otherwise specified, the medications summary tables will include the following columns: SEP-363856 50 to 100 mg/day, Quetiapine XR 400 to 800 mg/day, and Total.

Medications will be coded to Anatomical Therapeutic Chemical (ATC) Levels and Preferred Names according to World Health Organization Drug (WHODRUG) dictionary, Version 01MAR2019.

Whenever available, the time information should be accounted for in the derivation of prior, concomitant, and post-treatment medications. See [APPENDIX 2](#) for the handling of partial dates for medications. In the case where it is not possible to define a medication as prior, concomitant, or post treatment, the medication will be classified by the worst case, i.e. concomitant.

- Prior medications are medications which stopped prior to the first dose of study medication.
- Concomitant medications are medications which started at the same time of or after the first dose of study medication and at the same time of or before the last dose of study medication; or started prior to and ended at the same time of or after the first dose of study medication; or started at the same time of or prior to the last dose of study medication and marked as ongoing.
- Post-treatment medications are medications which started after the last dose of study medication.

Prior and concomitant medication use will be summarized by ATC Level 3 and Preferred Base Name for the SAF population by the actual treatment group. Medications will be sorted by ATC Level 3 alphabetically and by Preferred Base Name in decreasing frequency in the “SEP-363856 50 to 100 mg/day” column.

Prior, concomitant, and post-treatment medications will be provided in data listings.

Psychotropic and/or Sedating Medications taken by subjects prior to each visit as collected on the “*Timing of last dose of Psychotropic and/or Sedating Medications*” CRF form will be summarized by ATC Level 3 and Preferred Base Name for the SAF population by the actual treatment group and visit.

Document: **CCI**

Author: **PPD**

Version Number: 0.6

Version Date: 30JAN2023

Template No.: CS_TP_BS016 Revision 6

Reference: CS_WI_BS005

Effective Date: 02Dec2019

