16.1.1.4. Subgroup Analyses of PANSS Total Score

For each of the subgroup factors listed in [Section 7.5](#), change from Baseline in PANSS total score at Week 52 will be analyzed using the MMRM method. For the subgroup factors other than country, the MMRM model will include fixed effects for treatment, subgroup, visit, country, Baseline PANSS total

Document: CCI

Author: PPD

Version Number: 0.6

Version Date: 30JAN2023

Template No.: CS_TP_BS016 Revision 6

Reference: CS_WI_BS005

Effective Date: 02Dec2019

score, and treatment-by-subgroup, treatment-by-visit, subgroup-by-visit, and treatment-by-subgroup-by-visit interactions. For the subgroup factor of country, the MMRM model will include fixed effects for treatment, country, visit, Baseline PANSS total score, and treatment-by-country, treatment-by-visit, country-by-visit, and treatment-by-country-by-visit interactions.

Subgroups that do not have at least 2 EFF population subjects with change from Baseline in PANSS total score data available at Week 52/Visit 17 in each of the two treatment groups will be excluded from the analysis.

Estimates obtained from the MMRM model will be presented separately for each subgroup. The nominal p-value for the treatment-by-subgroup interaction at Week 52/Visit 17 will be presented. The presence of a significant interaction effect will be assessed at the 0.10 level for homogeneity of the treatment effect across the different categories of a subgroup factor. In case of a significant interaction effect, estimates by subgroup will be examined to determine the nature of the interaction (qualitative or quantitative). The MMRM results of all subgroup analyses will also be presented using forest plots.

The observed PANSS total score and the change from Baseline values will also be summarized descriptively by treatment group and visit for each subgroup.

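### The by-medication MMRMs for AIMS, BARS and SAS condition on a post-randomisation response to the symptoms being scored, so their treatment contrasts are not randomised comparisons

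*SAP*

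**What the plan says.** SAP 17.6.2 (AIMS total), 17.6.3 (BARS total) and 17.6.4 (SAS mean) each plan an all-subject MMRM and an ANCOVA. Each then adds an MMRM "performed for subgroups of subjects based on whether the subject took concomitant medications for treatment of movement disorders during the study", described as similar to the model in 16.1.1.4. AIMS scores are also to be "summarized descriptively by the subgroups of concomitant medication use for treatment of movement disorders", with parallel tables for BARS and SAS. One safeguard is given, in 17.6.2: "The list of medications will be determined by a review of the coded medication terms before database lock and study unblinding".

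Section 16.1.1.4 is the PANSS subgroup analysis. Its model has treatment-by-subgroup and treatment-by-subgroup-by-visit terms. Its reporting rules are "Estimates obtained from the MMRM model will be presented separately for each subgroup" and "The nominal p-value for the treatment-by-subgroup interaction at Week 52/Visit 17 will be presented", with the interaction judged at the 0.10 level.

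Three other passages determine who counts as a user:

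- SAP 13: "Concomitant medications are medications which started at the same time of or after the first dose of study medication" (and no later than the last dose). Drugs begun earlier and continued past the first dose also count.
- Protocol 10.3.1: "Treatment with medications used to treat movement disorders must be discontinued at least 1 day prior to randomization".
- Protocol 10.3.5: "Medications used to treat motor symptoms should not be given prophylactically". The same paragraph allows these drugs to be restarted if symptoms appear after randomisation.

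**The concern.** A subgroup contrast keeps the protection of randomisation only if membership is fixed before treatment can influence it. Here membership depends mainly on whether a subject developed motor symptoms on study drug and was treated for them, and AIMS, BARS and SAS score those same symptoms. If the two drugs differ in how often they cause such symptoms, the users in one arm are a different kind of subject from the users in the other, and the same holds for non-users. The contrasts then mix a treatment effect with a difference in case mix, and an interaction p-value would test for differences between two such mixtures.

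Timing adds to the problem. The flag covers the whole study, while the models estimate Weeks 1, 4, 24 and 52. A subject first medicated at Week 40 is already a user at Week 1, so the early contrasts condition on later events. Subjects who stay longer also have more time to become users.

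Printed in the 16.1.1.4 format, the output would read as the effect against quetiapine XR with and without anti-EPS medication. It does not estimate that.

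**Working it through.** The plan states no figure for this analysis, so there is none to reproduce. The first step is to read the texts together; the second is to illustrate what can happen.

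**Texts.** Drugs stopped before randomisation, no prophylaxis and restart on symptoms mean that use is mainly post-randomisation and symptom-driven. There are exceptions: drugs continued across the first dose (SAP 13), and drugs with other permitted uses, such as diphenhydramine for insomnia or beta-blockers for hypertension (Protocol 10.3.4 and 10.3.5). The subgroup factors in SAP 7.5 are geographic, demographic, history or baseline-type; this one is not among them. Sections 17.6.2 to 17.6.4 carry no caveat.

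**Illustration 1 (every input is assumed).** Let d be the mean score increase in a subject with EPS. Working in multiples of d makes the results apply to all three scales.

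- p = EPS rate: 0.15 in one arm, 0.05 in the other
- m = share of affected subjects medicated: 0.5 or 0.8
- b = share of unaffected subjects medicated: 0, 0.02 or 0.05
- r = share of d removed by medication: 0, 0.5 or 1
- m, b and r are the same in both arms

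Proportion of users: u = p·m + (1−p)·b. Mean scores:

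- users: p·m·(1−r)/u
- non-users: p·(1−m)/(1−u)
- all subjects: p·(1−m·r)

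Worked case, m = 0.8, b = 0.02, r = 0:

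- u = 0.12 + 0.017 = 0.137 and 0.04 + 0.019 = 0.059
- users: 0.12/0.137 − 0.04/0.059 = 0.876 − 0.678 = 0.198
- non-users: 0.03/0.863 − 0.01/0.941 = 0.035 − 0.011 = 0.024
- all subjects: 0.15 − 0.05 = 0.100

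Differences between arms, in multiples of d:

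| | m = 0.8 | m = 0.5 |
|---|---|---|
| Users, r = 0; b = 0 / 0.02 / 0.05 | 0 / 0.198 / 0.281 | 0 / 0.247 / 0.293 |
| Non-users, any r; b = 0 / 0.02 / 0.05 | 0.024 / 0.024 / 0.025 | 0.055 / 0.056 / 0.058 |
| All subjects; r = 0 / 0.5 / 1 | 0.100 / 0.060 / 0.020 | 0.100 / 0.075 / 0.050 |

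User differences halve at r = 0.5 and are 0 at r = 1. Over the 18 combinations, the ratio to the all-subject difference is 0 to 2.93 for users (0.293/0.100 at the top) and 0.24 to 1.24 for non-users (0.024/0.100 to 0.025/0.020). The user contrast can also equal the all-subject one: with m = 0.8 and b = 0.02, solving 0.198(1−r) = 0.100 − 0.080r gives r = 0.83, both 0.034. With p = 0.10 in both arms, all three differences are 0 for every m, b and r.

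**Illustration 2 (a different model, also assumed).** This is a simulation of 200 vs 100 subjects (300 at 2:1), 4,000 runs per scenario. Latent severity has SD 1. Medication starts when severity plus noise (SD 0.5) exceeds 1.2. Outcome noise has SD 0.3, and medication has no effect on the score. The treatment effect is identical in every subject.

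| True difference | Use, SEP-363856 vs quetiapine XR | All subjects | Users | Non-users |
|---|---|---|---|---|
| 0 | 14% vs 14% | 0.00 | 0.00 | 0.00 |
| −0.30 | 9% vs 14% | −0.30 | −0.10 | −0.23 |
| −0.60 | 5% vs 14% | −0.60 | −0.20 | −0.47 |

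If medication lowers the score by 0.5, the all-subject differences become −0.27 and −0.56, while the subgroup contrasts barely move. Neither subgroup recovers the effect, although the effect is homogeneous by construction.

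**The case against.** The strongest reply concerns weight. This is a supplementary safety analysis in a study with no comparative hypothesis; Protocol 15.3.6.8 leaves extra movement-scale analyses to the SAP, and SAP 7.4 calls all p-values nominal. That stands and limits the importance of the point. Nominal status deals with multiplicity, though, not with loss of comparability.

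The interaction test is also inferred: 17.6.2 to 17.6.4 refer to the model in 16.1.1.4 and do not say that its reporting rules follow. That stands too, so the point about the test is conditional. The subgroup contrasts are the purpose of the added model in any case.

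The magnitudes have no source in the documents. The exact zero for users without background use arises because every affected subject is given the same d, and the top of the range needs 5% of unaffected subjects to count as users. Both are fair; the figures show possibility, not expected size. Some restarts will reflect a pre-study need, since only moderate or severe movement disorder is excluded at entry, but the restart still happens after randomisation.

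Finally, if a label is enough for the descriptive tables, it could be enough for the model. Labelling the model would be second best. The tables show observed scores, whereas the model produces an adjusted treatment difference that has no treatment-effect interpretation here. Fixing the drug list before unblinding is worth keeping, but it prevents selective choice of drugs and does not make membership a baseline factor.

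**Conclusion.** The concern holds. The by-medication MMRM contrasts for AIMS total, BARS total and SAS mean are not randomised comparisons, and the SAP does not say so. The conclusion rests on the protocol's rules for these drugs and the SAP's definition of concomitant medication, not on the illustrations. Bias arises if treatment affects symptoms or medication use, and is zero if it affects neither. Its size and direction cannot be derived from the documents; under the assumed inputs the user contrast can lie below, at or above the all-subject difference. The primary endpoint, the all-subject MMRM and ANCOVA, the AIMS and SAS shift tables and the EPS odds ratio are unaffected. This should be changed, but nothing central to the trial depends on it.

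**What to change.** In SAP 17.6.2, 17.6.3 and 17.6.4:

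- Delete the by-medication MMRM and any interaction test carried over from 16.1.1.4.
- Keep the by-medication descriptive tables and the drug list fixed before unblinding. Label each table: *post-randomisation subgroup, not a randomised comparison*.
- Add one summary row giving the number and percentage of subjects in each arm who used any listed movement-disorder medication. SAP 13 tabulates concomitant drugs by ATC level 3 and base name, but not as one group. Unlike the subgroup contrasts, this is a comparison of the arms as a whole.

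The cost is SAP wording, one supplementary model fewer per scale and one extra row. What is lost is a model-based estimate by medication use; the descriptive tables still show those scores. No data collection or clinical rule changes.

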17.6.3 BARNES AKATHISIA RATING SCALE (BARS)

The BARS is a rating scale geared toward assessment of neuroleptic-induced akathisia, though it can be used to measure akathisia associated with other drugs as well. The BARS consists of four items, including one item assessing objective restlessness (item 1), two items targeting subjective restlessness

Document: CCI

Author: PPD

Version Number: 0.6

Version Date: 30JAN2023

Template No.: CS_TP_BS016 Revision 6

Reference: CS_WI_BS005

Effective Date: 02Dec2019

(awareness and related distress; items 2 - 3), and one global clinical assessment of akathisia item (item 4). The objective and subjective items are anchored and utilize a 4-point scale. The global assessment item has a 6-point scale (from absence of akathisia through severe akathisia).

The BARS total score is the sum of items 1 through 3 and ranges from 0 to 9. Higher values of the BARS total score indicate higher severity of akathisia. If one or more of items 1 to 3 are missing at a visit, the BARS total score will be set to missing for that visit.

The post-Baseline BARS Global Clinical Assessment of Akathisia responses will be classified as 'worsened', 'unchanged', or 'improved', relative to a subject's Baseline response to this item. A higher score than that of the Baseline would be classified as 'worsened'. Conversely, a lower score would be classified as 'improved'. If the score is equal to that of Baseline, the score will be classified as 'unchanged'.

BARS is assessed at these study visits: Visit 2, Visit 3, Visit 5, Visit 10, and Visit 17.

Change from Baseline in BARS total score at each scheduled visit (Week 1/Visit 3, Week 4/Visit 5, Week 24/Visit 10, Week 52/Visit 17) will be analyzed using an MMRM similar to the model described in [Section 16.1.1.1](#) with Baseline BARS total score as the covariate. In addition, the MMRM analysis will be performed for subgroups of subjects based on whether the subject took concomitant medications for treatment of movement disorders during the study, which is similar to the model described in [Section 16.1.1.4](#).

Change from Baseline in BARS total score at each scheduled visit (Week 1/Visit 3, Week 4/Visit 5, Week 24/Visit 10, Week 52/Visit 17) will be analyzed using an ANCOVA model similar to the model described in [Section 16.1.1.3](#) (Analysis of covariance (including LOCF)) with Baseline BARS total score as the covariate.

The observed BARS total score and the change from Baseline values will also be summarized descriptively by treatment group and visit. In addition, the observed BARS total score and the change from Baseline values will be summarized descriptively by the subgroups of concomitant medication use for treatment of movement disorders.

Change from Baseline in BARS global clinical assessment score at each scheduled visit (Week 1/Visit 3, Week 4/Visit 5, Week 24/Visit 10, Week 52/Visit 17) will be analyzed using MMRM and ANCOVA models similar to the model described in [Section 16.1.1.1](#) and [Section 16.1.1.3](#) (Analysis of covariance (including

Document: **CCI**

Author: **PPD**

Version Number: 0.6

Version Date: 30JAN2023

Template No.: CS_TP_BS016 Revision 6

Reference: CS_WI_BS005

Effective Date: 02Dec2019

LOCF)), with Baseline BARS global clinical assessment score as the covariate.

Lastly, the observed BARS item scores and the change from Baseline values will be summarized descriptively by treatment group and visit. In addition, the frequency distribution of each BARS item will be summarized descriptively by treatment group and visit. Post-Baseline changes in BARS global clinical assessment score (Worsened/Unchanged/Improved) will be summarized descriptively by treatment group and visit.

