^r Unscheduled BARS, AIMS, and SAS scales should be administered if a subject develops extrapyramidal symptoms (EPS) requiring treatment.

^s To be completed at the Screening Visit only for those subjects who were currently treated with an antipsychotic medication.

^t Events occurring prior to first dose of study drug are programmatically identified as pretreatment events. Events occurring after first dose of study drug are programmatically identified as adverse events.

^u Duplicate subject check will be performed (where allowed by local/regional regulations). Subject consent is required.

^v The PANSS-Informant Checklist (PANSS-IC) form will be completed as part of the PANSS.

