4.3. Risk-Benefit Assessment

Schizophrenia is a lifelong disorder and despite advances in drug treatment many patients continue to experience significant symptoms, disabling side effects and impaired functioning and quality of life. Some patients respond poorly to currently available antipsychotics and continue to have symptoms and substantial functional/cognitive impairment ([Keefe-2006](#); [Webber-2008](#)).

Antipsychotic treatment is associated with medically-important adverse effects, including weight gain, metabolic syndrome, sedation, extrapyramidal symptoms (including akathisia), hyperprolactinemia and QT interval prolongation ([Davis-2004](#); [Lieberman-2005](#); [Newcomer-2007](#); [Leucht-2009](#)). These side effects are attributable to both on-target (D₂) and off-target receptor binding. A significant unmet need still exists for treatments with better efficacy, safety and tolerability.

SEP-363856 has a novel mechanism of action and does not functionally modulate the D₂ receptor nor any of the receptors shown to impart significant side effects of currently approved antipsychotics.

In an adequate and well-controlled four-week double-blind study in adults with schizophrenia (Study SEP361-201), SEP-363856 demonstrated a statistically significant improvement in Positive and Negative Syndrome Scale (PANSS) total score compared to placebo with an effect size of 0.45, supporting antipsychotic efficacy. The effectiveness of treatment with SEP-363856 was also shown to be sustained over a 6-month extension period (Study SEP361-202). Overall, the safety and tolerability profile of SEP-363856, including rates of extrapyramidal symptoms and hyperprolactinemia, was comparable to placebo. Notably, no clinically significant mean changes from baseline in lipid or glucose parameters were found, nor was weight gain observed in association with SEP-363856 treatment.

SEP-363856 has the potential to provide a significantly improved safety profile compared to available therapy, while providing efficacy in the treatment of patients with schizophrenia. Data generated in the clinical program to date provide an acceptable expected benefit/risk ratio for evaluating SEP-363856 in adults with schizophrenia in this study.

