6.4. RETESTS, UNSCHEDULED VISITS, AND EARLY TERMINATION DATA

In general, for by-visit summaries, data recorded at the planned visits where assessment is intended to be given and collected within 9 days post last dose will be presented, as well as the derived Baseline value and the LOCF value.

Unscheduled measurements will not be included in by-visit summaries as a separate time point. Unscheduled measurements collected prior to the first dose of study medication will contribute to the derivation of the Baseline value. Unscheduled measurements collected post Baseline up to and including 9 days after the last dose of study drug will contribute to the derivation of the LOCF value, the potentially clinically significant (PCS) value, and the best/worst case value where required (e.g. shift table).

In the case of a retest, the assessment recorded under the planned visit will be used for by-visit summaries, and the assessment(s) recorded under unscheduled visit(s) will be presented in listings only.

As per protocol, study Visit 17 can be a Week 52/End of Treatment (EOT) visit or an Early Termination (ET) visit. If a subject terminates early, his/her measurements taken at the ET visit and within 9 days post the last dose will be mapped to the next planned visit (after the last scheduled visit the subject attended)

Document: CCI

Author: PPD

Version Number: 0.6

Version Date: 30JAN2023

Template No.: CS_TP_BS016 Revision 6

Reference: CS_WI_BS005

Effective Date: 02Dec2019

during which that assessment was expected to be performed as specified by the Schedule of Assessments table in the protocol. This applies to both efficacy and safety data. ET measurements taken beyond 9 days post the last dose will not be mapped.

Listings will include scheduled, unscheduled, retest, and early discontinuation data without regard to the 9-day window, with original dates and visits displayed.

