Shift from Baseline in SAS mean score category (Normal/Abnormal) to each post-Baseline scheduled visit (Week 1/Visit 3, Week 4/Visit 5, Week 24/Visit 10, Week 52/Visit 17) and to the overall post-Baseline period (including both the double-blind treatment period and the follow-up period up to and including 9 days after the last dose of study drug) will be summarized descriptively by treatment group.

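### SAP 17.6.3 gives BARS no overall post-Baseline summary, so a rating triggered by treated extrapyramidal symptoms is tabulated only if it happens to be the LOCF value

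*SAP*

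**What the plan says.** The protocol (Table 2, footnote r) sets the trigger: "Unscheduled BARS, AIMS, and SAS scales should be administered if a subject develops extrapyramidal symptoms (EPS) requiring treatment". The footnote does not name akathisia, but the Risk-Benefit Assessment (Protocol 4.3) counts it within EPS, writing of "extrapyramidal symptoms (including akathisia" in a parenthesis. Change from Baseline in BARS is a listed safety endpoint (Protocol 6.2).

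The scheduled ratings are few: "BARS is assessed at these study visits: Visit 2, Visit 3, Visit 5, Visit 10, and Visit 17" (SAP 17.6.3).

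SAP 6.4 governs unscheduled data. On tables by visit it says: "Unscheduled measurements will not be included in by-visit summaries as a separate time point". Unscheduled measurements after Baseline and up to 9 days after the last dose "will contribute to the derivation of the LOCF value, the potentially clinically significant (PCS) value, and the best/worst case value where required", with a shift table given as the example.

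SAP 17.6.3 then specifies for BARS an MMRM, an ANCOVA that includes LOCF, descriptive summaries of the total and items, subgroup summaries by use of movement-disorder medication, and a change table for the global item: "Post-Baseline changes in BARS global clinical assessment score (Worsened/Unchanged/Improved) will be summarized descriptively by treatment group and visit". It describes no summary over the whole post-Baseline period.

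The other two movement scales do have one. SAP 17.6.2 plans a "Shift from Baseline in AIMS total score category (Normal/Abnormal) to each post-Baseline scheduled visit", and SAP 17.6.4 a "Shift from Baseline in SAS mean score category (Normal/Abnormal) to each post-Baseline scheduled visit". Both sentences go on to add the overall post-Baseline period, which covers treatment and follow-up through 9 days after the last dose.

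**The concern.** The protocol asks for a BARS at the moment of most interest, when EPS is bad enough to treat, and the analysis plan has almost nowhere to put it. Protocol 10.3.5 allows as-needed treatment of EPS and akathisia, so by the next scheduled rating the episode may have gone. The BARS tables would then describe the subject before and after the episode but not during it.

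Akathisia is one of the class effects that the protocol names, and the comparator is an antipsychotic. A reader of the study report who turns to the BARS tables to see how severe akathisia became in each arm would not find the ratings collected for that purpose. The adverse event tables would show that an event occurred, graded mild, moderate or severe by the investigator, but not its score on the scale.

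**Working it through.** No sample-size, power or alpha figure bears on this point. The check is to find the rating gaps and then follow one unscheduled rating through the SAP.

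**Gaps between scheduled ratings.** Study days come from Protocol Table 2; the BARS visits from SAP 17.6.3.

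| Interval | Days | Gap |
|---|---|---|
| Visit 2 to Visit 3 | 1 to 8 | 8 − 1 = 7 |
| Visit 3 to Visit 5 | 8 to 29 | 29 − 8 = 21 |
| Visit 5 to Visit 10 | 29 to 169 | 169 − 29 = 140 |
| Visit 10 to Visit 17 | 169 to 365 | 365 − 169 = 196 |

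The last two gaps add to 140 + 196 = 336 of 365 − 1 = 364 days, or 92% of the scheduled period. This is a share of calendar time, not of episodes.

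**Following one rating.** Take a subject rated on an unscheduled BARS between Days 29 and 169 because EPS needed treatment, who has recovered by Day 169.

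1. *By-visit summaries, MMRM and by-visit ANCOVA.* SAP 6.4 excludes the rating as a time point. The Week 24 row shows the recovered score, and the global item can read Unchanged.
2. *PCS value.* SAP 6.4 would admit the rating, but no BARS criterion appears in SAP 17.3.2, 17.4.2 or Appendix 8.
3. *Best/worst-case value.* SAP 6.4 would admit it where such a value is required. SAP 17.6.3 requires none.
4. *LOCF.* SAP 6.3 derives a BARS LOCF endpoint from scheduled, unscheduled and early-termination ratings up to Visit 17 and within 9 days of the last dose, taking the last one with a total score. The LOCF ANCOVAs of BARS total and global score use it. Here the Week 24 rating is later, so the event rating is displaced. In general it survives only if no later qualifying rating exists, for example when the end-of-treatment or early-termination BARS is missing, incomplete or out of window.
5. *Listings.* The rating is listed (SAP 6.4).

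**The three scales side by side.**

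| | AIMS (17.6.2) | SAS (17.6.4) | BARS (17.6.3) |
|---|---|---|---|
| Normal/Abnormal cut-off defined | yes | yes | no |
| Shift to overall post-Baseline period | yes | yes | no |
| Worsened/Unchanged/Improved for global item | by visit | no global item described | by visit |
| Stated that unscheduled ratings count in the shift | no (follows from 6.4) | no (follows from 6.4) | not applicable |

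Elsewhere in the safety plan, summaries over the whole post-Baseline period expressly include unscheduled visits: laboratory PCS values (17.2), QTc and ECG criteria (17.3), vital-sign PCS values and orthostatic events (17.4) and C-SSRS (17.6.1).

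**The case against.** The case for leaving SAP 17.6.3 alone has several sound parts.

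- *The rating is not shut out altogether.* A reader might infer that unscheduled BARS ratings enter no BARS table. SAP 6.3, 6.4 and 17.6.3 do not support that: LOCF can use them. This stands, and it limits the point to ratings followed by a later one.
- *Early terminators are rated.* BARS is due at early termination, and SAP 6.4 maps that rating, if within 9 days of the last dose, to the next planned BARS visit. The sample-size text expects about 80 completers on SEP-363856. With 300 × 2/3 = 200 randomised to that arm, 80/200 = 40% would complete and about 60% would leave early. An episode that ends in withdrawal is thus likely to be rated and tabulated. This stands. The same rating, however, displaces an earlier unscheduled one as the LOCF value.
- *There is a reason for the asymmetry.* The AIMS and SAS shifts rest on cut-offs that the SAP does not define for BARS, and the AIMS global item is also summarised by visit only. A reader might infer that 17.6.2 and 17.6.4 already contain worst-score tables to be copied across. They do not: each has a category shift, and neither states which value represents the overall period. This bears on how the fix is worded. It does not close the gap, because the BARS global item needs no cut-off to be shifted.
- *The event is reported elsewhere.* Extrapyramidal adverse events, with akathisia among the search terms (Appendix 4), are tabulated by preferred term and compared by odds ratio. All adverse events are also shown by maximum severity, and BARS is summarised by use of movement-disorder medication. This stands, although that BARS subgroup summary draws on the same by-visit ratings.
- *Worst values are not neutral.* They rise with the number of ratings and the time on study. This stands as a caution about presentation.

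**Conclusion.** The gap is real and modest in size. An unscheduled BARS taken because EPS required treatment enters no BARS summary unless it becomes the LOCF value, and BARS alone of the three movement scales has no summary over the whole post-Baseline period. What can be lost is the peak rating of an episode that is treated and resolves inside the 140-day or 196-day gap. The primary adverse event endpoint is unaffected.

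Two stronger conclusions might be inferred and should not be. The 92% of calendar time in the two long gaps is not the share of episodes missed: the documents give no rate or timing of episodes, early-termination ratings are tabulated, and an episode still present at Week 24 or 52 is rated there. Nor do the documents show that the omission always moves the comparison towards no difference. It hides resolved peaks in both arms, and the effect on the contrast depends on episode rates that are not given.

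The conclusion rests on two readings: that akathisia counts as EPS for footnote r, as Protocol 4.3 implies, and that SAP 6.4 applies to BARS as written.

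**What to change.** In SAP 17.6.3, add one descriptive table by arm for the overall post-Baseline period, through 9 days after the last dose and including unscheduled ratings. It should show:

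- the worst BARS global clinical assessment score, as a shift from Baseline and as Worsened/Unchanged/Improved under the definitions already in that section;
- the worst BARS total score, with its change from Baseline.

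No new cut-off is needed. In SAP 17.6.2 and 17.6.4, state that the overall-period shifts for AIMS and SAS include unscheduled assessments, so that all three scales follow one explicit rule.

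The cost is one table and two clarifying phrases, from data already collected, with no change to visits or models. The drawback is that worst values depend on how many ratings a subject has and how long the subject stays in the study. The table should therefore carry no test, should be shown alongside exposure in each arm, and should leave the by-visit analyses as they are.
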